Subjects: Subjects from the age of 16 years with documented diagnosis of asthma and/or COPD, daily treated with dry powder inhaler (DPI) or metered dose inhaler (MDI), or both, will be invited to voluntarily participate. Exclusion criteria is age <16 years, no access to use BankID or similar electronic personal identification service, not using smartphone of type Android or iPhone, plan to stop use DPI and/or MDI the following 6-12 weeks from inclusion. No able to independently handle and inhale through DPI or MDI device.

Total sample size: Eighty subjects (females and males) with daily treatment for COPD or asthma will be sufficient, based on the assumption of 25% percentage improvement in success rate of correct

inhalation technique in the interventional group compared with control group (75% versus 50%) with 80% power at 5% significance level, including dropouts at 6-12 weeks follow-up visit.

Intervention: At the baseline visit patients will be randomised to app-based intervention consisting of education and training of inhalation technique of all inhalers used on daily basis (the inhalation app-module). Stratified randomisation based on type of inhaler(s); MDI, DPI or both MDI and DPI will be applied. The intervention is the inhalation app-module, which is a medical device that is embedded the AsthmaTuner app. The AsthmaTuner app is a CE-marked cloud-based system, provided by MediTuner AB in Stockholm, Sweden. The intervention group will be instructed to use the inhalation app-module on daily basis to improve their inhalation technique.

Control group: Standard education of inhalation technique using list of standardised criteria and non-app-based education of inhaler technique.

Endpoints: Primary endpoint is the rate of subjects with successful inhalation techniques based on subjective critical endpoints (CIP Table 2) and the following objective endpoints at the 6-12 weeks follow up visit:

- DPI: PIF \geq 30 L/Min, time to PIF <0.5 seconds measured with the investigational device.
- MDI: inspiration time (> 3 seconds) and PIF less than 60 L/Min measured with the investigational device.

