11	For Handyhaler or similar, check powder drug rests in capsule, if necessary, inhale again	Breathed out and away from the mouthpiece of the inhaler

Each subject in both intervention and control arm will receive standard assessment and instruction on inhalation technique according to criteria in Table 2 at baseline visit. The study endpoints will be collected at the follow-up visit (6-12 weeks).

Randomisation and masking

Each of the 80 subjects is stratified to block of 4 numbers according daily used inhaler of (1) DPI, (2) MDI or (3) both MDI/DPI. Simple randomisation (1 to 1) will be applied in each block and at each study site. The randomisation will be blinded for the evaluator at 6-12 week visit, which practically means that not the same study personnel will do the baseline randomisation and the final 6-12 weeks assessment of inhalation technique.

Endpoints

Primary endpoint is number of subjects presenting successful inhalation techniques as defined by objective endpoints divided by:

- DPI: PIF \geq 30 L/Min, time to PIF <0.5 seconds measured with the investigational device.
- MDI: inspiration time (> 3 seconds) and PIF less than 60 L/Min measured with the investigational device.
- Together with subjective critical endpoints at 6–12-week follow-up visit, assessed by study personnel, Table 2.

Secondary endpoints:

- Feasibility and safety of using the investigational device for education and training of inhalation technique based on questionnaire and interviews from subjects and healthcare personnel, Appendix 3.

Study personnel will get access and be trained in methods and procedures for informed consent, randomisation, investigational device, data collection and documentation. The study endpoints will be documented in electronic Case Report Form (CRF) provided by Karolinska Institutet. Data analysis will start as soon as all 80 included subjects have completed or considered to be lost to follow-up at 6-12 week's visit by local investigator.

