Subjects lost to follow-up will not be replaced but the decision will be documented in the medical record. Subjects who not attend the follow-up visit 12 weeks after the baseline visit will be categorised as lost to follow-up. They will be asked through email, phone or letter to send in the medical device to the study centre with envelope they received when they received the device at baseline visit. Study sites will be informed about which subjects were lost to follow-up.

Point of enrolment and randomisation

At least 80 subjects will be invited to participate in the investigation, through phone, digital meeting (Teams or Zoom or similar) or at physical at the baseline visit. The study personnel at investigational site will contact the study centre through phone to receive the randomisation assignment and study ID. The anticipated distribution is a minimum of 10 subjects per each participating investigational site.

Expected duration of each subject's participation is 6-12 weeks after enrolment to the investigation. The follow-up visit will be booked 6 weeks after study enrolment but no longer than 12 weeks. Subjects unable to attend the 6-12-week follow-up visit will be withdrawn from the primary analysis of study. The number of subjects required to be included in the investigation is estimated on background of power calculation (see section A7). The timeline is to enrol subject to the investigation during the fall of 2024 and spring of 2025. No additional care is required after the investigation beyond what was initially planned for each subject.

Target and vulnerable populations

The target population for the medical device are patient treated for asthma or COPD or any other disorder requiring treatment with DPI or MDI in primary or secondary care setting. However, neither patient with other diagnosis or children under the age of 16 years will not be included in the study. Although schoolchildren below the age of 16 are considered as target populations for the medical device, we consider we have sufficient data from this population from the pilot study (Appendix 4). Vulnerable, pregnant and breastfeeding population fulfilling the inclusion criteria are welcome to participate, no adverse effects or events are expected in this vulnerable population as longs they will be able to attend the follow-up visit.

A.6.4 Procedures

The subjects will undergo the following procedures as summarized in Table 3.

Procedures	Baseline visit	6–12-week follow-up visit

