Informed consent	X	
Randomization	X	
Questionnaires of medical history and usability	X	X
Spirometry test	X	
Standard review and correction of inhalation technique	X	X
Objective assessment of inhalation technique		X
Adverse events or device deficiency		X

Randomisation

Computer-based randomisation stratified for subjects' daily inhaler use into three groups of DPI, MDI or both DPI and MDI devices of four block numbers in each stratum per investigational site.

Interview and electronic questionnaires

- A structured health questionnaire completed at the first visit will provide information regarding medical history, health care utilization and experiences of inhalation education and training, Appendix 4.

Dynamic spirometry

- The lung function test will measure forced expiratory flow in one second (FEV₁), forced vital capacity (FVC), and FEV₁/FVC according standardised procedures [31]. Applied percent of predicted reference values, adjusting for age, sex, height, weight and ethnicity, will be calculated based on continuous prediction equations of normal population [32].

Standard review of inhalation technique

- All subject's ability to handle their inhaler(s) and inhalation technique will be reviewed and corrected at baseline visit and assessed at 6–12-week follow-up visit according to endpoints in Table 2.

Investigational device - app-based intervention for education and training of inhalation technique

1. Subjects randomised to intervention will receive instructions on using the investigational device, accompanied with written information (instructions for use) from study personnel at baseline visit. The subjects are instructed to use the investigational device 3-7 times per week to achieve the maximal effect.

2. Instruction for use manual on how to use medical investigational device will be available for subjects and study personnel at investigational sites (Appendix 5). Briefly, subjects follow the following procedure:
 - a. Baseline visit: Download (Apple Store or Google Play) and login with BankID or similar to the AsthmaTuner app. Automatic Bluetooth connection will be established between the MIR AsthmaTuner and the app.
 - b. Study personnel at Karolinska institutet set up login through BankID or SITHS card to AsthmaTuner Careportal for study personnel at investigational site.
 - c. Enter patient information: Fill out patient's initial letters, study ID, height, weight and type of inhaler. Press "next" to start the test.

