The subjective assessment of inhalation will be conducted ‘blinded’ by study personnel. The assessment will be filmed through Teams or Zoom to facilitate standardised review and judgment of inhalation technique according to Table 2. The film is stored on local hard disk of the computer and will be deleted after the “blinded” assessment is done.

The objective assessment will be performed in both groups according to Figure 3 a-c. Data is stored in the AsthmaTuner cloud.

Compromising factors that might affect the outcomes are i.e. ongoing exacerbation (asthma or COPD), the follow-up visit can therefore be rescheduled within the time frame of 6-12 weeks in case of any medical condition is deemed to affect the study endpoints. The coordinating investigator will

take the decision to withdraw subject in case of any not resolved medical condition, not present at baseline visit, is judged to significantly affect inhalation technique or subject's safety at the follow-up visit.

A.6.5 Monitoring plan

Before the beginning of the investigation, the Sponsor will appoint an independent monitor at Karolinska Trial Alliance (KTA). Monitoring will be performed before, during the study and after the study is completed in accordance with the ISO 14155 GCP (Good Clinical Practice) standard. Study conductance, source data, device accountability, adherence to the study protocol, Good Clinical Practice, and regulatory requirements will be monitored.

Data to be monitored at site are e.g.

- Patient information and Informed Consent. That each patient included in the study has signed an Informed Consent and that no study procedures have begun before the date of the consent.
- That inclusion criteria are met for the included patients
- That all types of adverse events and serious adverse events, device related or not, as well as, those that might have led to SAE shall be reported, and even if those are listed as expected in this Clinical Investigation Plan.
- Check that all CRF data are entered
- Other CRF data will be source data verified against patient records according to a detailed Monitoring Plan (that will contain details regarding the overall monitoring) signed by the Sponsor prior to the start of the study. At least 10% of the patients will have data in the CRFs 100% source data verified.

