The monitor and possible authorities must be given direct access to source documents (original documents, data and records). Direct access includes permission to examine, analyse, verify and reproduce any record(s) and report(s) that are important to the evaluation of the clinical study. In order to be able to do that, a written consent from each patient should be obtained. Additionally, a secrecy agreement between the monitor and the person responsible for patient records at the study site will be signed.

A.7 Statistical considerations

The analytical approach of this RCT is intention-to-treat, analyzing the effect of the investigational device across all randomized subjects with assessed inhalation technique at the 6–12-week follow-up visit. Additionally, a per-protocol analysis will be conducted on subjects who performed an inhalation test on average more than once per week during the study period, to evaluate the efficacy of education and training on inhalation technique between the intervention and control groups.

The null hypothesis of this investigation is no difference in success rate of inhalation technique between subjects assigned to intervention or control group. If the number of patients with inhalation technique deemed for correction differ significantly between intervention and control group at 5% significance level, the null hypothesis will be rejected. Based on our cross-sectional pilot study, 50% of in 40 patients with asthma demonstrated successful inhalations technique (Appendix 3), assuming +25% absolute change of correct inhalation technique in the intervention group compared with control group including 20% drop out rate, enrolment of at least 80 patients will be sufficient to reach 80% power at 5% significance level.

Primary analysis: The success rate of subjects with correct inhalation technique according to objective and subjective critical endpoints at the 6-12 weeks follow-up visit. The effect of the medical device on rate of successful inhalation technique will be determined across randomisation groups with logistic regression analysis as risk ratio (RR) with 95% confidence interval. No interim analysis will be performed.

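### The per-protocol rule of more than one inhalation test per week either leaves no controls or compares app users selected after randomisation with all controls

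*Protocol*

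**What the plan says.** A.7 makes intention-to-treat the main approach, "analyzing the effect of the investigational device across all randomized subjects with assessed inhalation technique" at the follow-up visit. It then adds that "a per-protocol analysis will be conducted on subjects who performed an inhalation test on average more than once per week during the study period", and states the purpose: "to evaluate the efficacy of education and training on inhalation technique between the intervention and control groups". It gives no separate criterion for controls and does not restrict the rule to the app arm.

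Elsewhere the protocol fixes what controls do:
- The synopsis (A.1.5) defines the control condition as "Standard education of inhalation technique using list of standardised criteria and non-app-based education of inhaler technique".
- A.6.4 gives the device instructions only to subjects randomised to the intervention.
- Table 3 in A.6.4 marks the row "Objective assessment of inhalation technique" at the follow-up visit only. The follow-up text adds: "The objective assessment will be performed in both groups according to Figure 3 a-c".
- A.6.2 allows manual flow meters in controls where a site already uses them, with no schedule.

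**The concern.** The test-frequency rule measures exposure to the intervention, and only one arm is given that exposure. The same sentence nevertheless uses the rule to define a set for comparing the two arms.

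That leaves two readings, and neither gives a sound comparison. If the rule applies to everyone, there is no control group. If it applies to the app arm alone, the app side is filtered on behaviour after randomisation and the control side is not. Any device effect is then mixed with the difference between people who keep training and people who do not.

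The direction of that difference is unknown. Keen users may have better technique anyway. But A.6.1 also allows training as the subject needs it, so subjects with poor technique may train more.

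At stake is a supplementary result, not the primary one. However, A.6.1 calls the trial confirmatory, A.7 presents this analysis as an efficacy comparison between arms, and nothing labels it exploratory.

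**Working it through.** The protocol gives no figure for the size of the per-protocol set or for expected adherence. The first step below uses the protocol's own schedule. The second is an illustration on stated assumptions.

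**Step 1. Can a control meet the rule?**

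Inputs: one scheduled objective test per control (A.6.4, Table 3 and follow-up text); 6 to 12 weeks of participation (A.6.3); threshold of more than 1 test per week (A.7).

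Rate = scheduled tests / weeks.
- One test: 1/12 = 0.08 to 1/6 = 0.17 per week.
- If single inhalations are counted and the visit holds three (assumed): 3/12 = 0.25 to 3/6 = 0.50.
- Three inhalations on each of two inhalers, for a subject using both types (assumed): 6/12 = 0.50 to 6/6 = 1.00, still not more than 1.

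The threshold needs at least 7 tests in 6 weeks or 13 in 12 weeks. No control reaches it through scheduled procedures.

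**Step 2. What if the rule applies to the app arm only?**

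Inputs from the protocol: 80 randomised 1:1, 20% dropout and 50% control success. So 80 × 0.8 = 64 are assessed, 32 per arm.

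Assumptions: no device effect, so success is 50% overall in each arm; a share *a* of the app arm qualifies; qualifiers differ from non-qualifiers by a gap *g* in success.
- Success in qualifiers = 0.5 + (1 − a)g
- Success in non-qualifiers = 0.5 − a·g
- False difference from controls = (1 − a)g
- False risk ratio = [0.5 + (1 − a)g] / 0.5

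The last column is the exact rejection rate of the two-sided 5% pooled two-proportion test, with the qualifiers at their rate against 32 controls at 50%.

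| Qualifiers (a) | Gap g | Qualifiers v non-qualifiers | False difference | RR | Rejects |
|---|---|---|---|---|---|
| 16 (0.50) | 0 | 50% v 50% | 0 | 1.00 | 5.2% |
| 16 | 10 points | 55% v 45% | 5.0 points | 1.10 | 6.4% |
| 16 | 20 points | 60% v 40% | 10.0 points | 1.20 | 10.2% |
| 16 | 30 points | 65% v 35% | 15.0 points | 1.30 | 16.7% |
| 24 (0.75) | 0 | 50% v 50% | 0 | 1.00 | 5.1% |
| 24 | 10 points | 52.5% v 42.5% | 2.5 points | 1.05 | 5.5% |
| 24 | 20 points | 55% v 35% | 5.0 points | 1.10 | 6.7% |
| 24 | 30 points | 57.5% v 27.5% | 7.5 points | 1.15 | 8.7% |

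With 20 qualifiers (a = 0.625), the rejection rates for gaps of 0, 10, 20 and 30 points are 5.0%, 5.8%, 8.2% and 12.3%.

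If qualifiers do worse, the rejection rates are the same but the false difference is −2.5 to −15 points (RR 0.95 to 0.70), and the rejections fall almost entirely against the device.

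If 90% qualify, the false difference is only (1 − 0.9) × 10 to 30 = 1 to 3 points. With 29 of 32 qualifying, the same test rejects in 4.8% to 5.3% of trials, against 4.7% with no gap.

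**The case against.** The best defence is that the authors meant an adherence filter on the app arm. Only that arm is told to use the device, and the sentence plainly expects controls in the comparison. On that view the empty control side is a drafting gap, closed by naming the intervention arm. This is probably the intent, but the edit only moves the plan to the second reading, where the selection is one-sided.

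A second point is that every per-protocol analysis conditions on events after randomisation, and that the protocol guards against this by making intention-to-treat primary. That is true and limits the weight of the finding. The specific fault is narrower: the criterion is one that only one arm can meet.

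A third is that details of analysis sets often belong in the SAP, which is not at hand. A missing control criterion alone would not be a finding. Here the protocol has already fixed a rule that fails as written, and an SAP could repair it only by changing it or adding to it.

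Two further points stand. The threshold is lenient against the use instructions in A.1.5 and A.6.4, so high adherence and a small bias are plausible. And the superiority claim in A.5 is not tied to the per-protocol set. The upper rejection figure is therefore not evidence of a likely false claim.

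**Conclusion.** The concern holds. Under the literal reading, no control qualifies through scheduled procedures. This rests only on the protocol's own schedule and needs no assumption about adherence. Under the app-arm-only reading, users selected after randomisation are set against all assessed controls.

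The size of the resulting bias is unknown, because the protocol gives neither the share qualifying nor the success gap. For the ranges assumed above it runs from negligible at about 90% qualifying to 15 points in either direction at 50% qualifying. The primary analysis is untouched. This should be corrected, but it does not threaten the trial's main result.

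**What to change.** In A.7, stop using the test-frequency rule to define a between-arm efficacy set. There are two ways to do this.

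1. Define the per-protocol set by criteria that apply equally to both arms: eligible, assessed within the 6-12 week window, allocated education received, and no cross-over to the app. State that this set will largely overlap the primary set. A.6.3 already says "Subjects unable to attend the 6-12-week follow-up visit will be withdrawn from the primary analysis of study", and A.6.1 says "Each subject in both intervention and control arm will receive standard assessment and instruction on inhalation technique" at baseline. State also that the set still conditions on events after randomisation.
2. Keep the usage threshold only for a descriptive, exploratory analysis within the app arm, and say that it does not support the superiority claim.

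Option 2 is simpler, because option 1 adds little to the primary analysis.

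The cost is a rewording of A.7. No new data are needed, since A.8 already has objective test data stored with time points. The downside is that there will be no between-arm estimate specific to regular app users.

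Separately, and not part of the weight of this point, the instructed frequency of app use differs between the synopsis (daily), A.6.1 (at least weekly, or as needed) and A.6.4 (3-7 times per week). A subject training exactly once a week meets A.6.1 but fails the threshold in A.7. These passages must be reconciled with each other and with any usage threshold that is kept, which needs edits outside A.7.

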A.4.E Steps that will be taken to control or mitigate the risks

The signed IB including the risk analysis shows all risk control options that have been implemented to mitigate the risks associated with the inhalation module.

A.4.F Rationale for benefit-risk ratio

The assumption is that the benefits of using the investigational device to improve inhalation technique in subjects with asthma and/or COPD compared with standard education outweigh the risks. The nature of the risk control options makes that there are no unacceptable residual risks, as all risks are identified as low. The expected benefit of the investigational medical device is to make materials and methods for training and education of inhalation technique more available and feasible to use for patient and HCP. Additionally, to make the support for inhaler use more accessible for patients at home or whenever patients feel inhalation support is needed. It is therefore that the manufacturer believes that the investigational device has a positive benefit-risk ratio and is safe to use for patients. However, the results of this clinical investigation will be considered, and the benefit-risk ratio will be reassessed after the clinical investigation has been completed.

A.5 Objectives and hypotheses of the clinical investigation

Our hypothesis is that the app-based investigational medical device consisting is superior for education and training of inhalation techniques in patients with asthma and COPD compared with standard care. The pre-clinical evaluation indicated the use of the investigational device is a feasible and safe for patients using inhaler(s) for treatment. The study assumption is that the investigational medical device will improve the relative rate of successful inhalation technique with at least 25% compared with control group.

Primary aim: To investigate if app-based education and training of inhalation technique improves the rate of successful inhalation techniques compared with control group at 6-12 weeks follow-up visit.

Secondary aims: To evaluate the usability and safety of the investigational device during the study period.

The claim that this clinical data can substantiate is: the inhalation app-module in AsthmaTuner is superior for education and training of inhalation techniques in patients with asthma and COPD, when compared to standard care.

There are no identified risks or anticipated adverse events that will be studied in this clinical investigation.

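### Eighty enrolled with 20% dropout gives about 55% power for 50% versus 75%, not the 80% stated

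*Protocol*

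**What the plan says.** Section A.7 takes its control rate from a pilot study ("50% of in 40 patients with asthma demonstrated successful inhalations technique (Appendix 3"), states the effect as "assuming +25% absolute change of correct inhalation technique in the intervention group compared with control group including 20% drop out rate", and concludes: "including 20% drop out rate, enrolment of at least 80 patients will be sufficient to reach 80% power at 5% significance level". The synopsis in A.1.5 gives the same contrast, "inhalation technique in the interventional group compared with control group (75% versus 50%) with 80% power at 5% significance level", and makes eighty the total sample size with dropouts already counted.

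Other sections fix how many subjects carry that power. A.6.1 assigns the 80 subjects 1:1 to two arms and starts the analysis once all 80 have completed or been lost. A.6.1 and A.6.3 withdraw from the primary analysis anyone who misses the follow-up visit and do not replace them, and A.7 analyses those whose technique was assessed.

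The null hypothesis in A.7 is worded without direction: "The null hypothesis of this investigation is no difference in success rate of inhalation technique between subjects assigned to intervention or control group". The number of sides of the test is not stated.

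Section A.5 words the effect differently, as an assumption that the device will "improve the relative rate of successful inhalation technique with at least 25% compared with control group".

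**The concern.** For 50% against 75%, a total of 80 including dropouts is well below what the standard two-proportion calculation gives at 5% significance and 80% power. Nothing in the protocol, such as a gain from covariate adjustment or a special test, accounts for the gap.

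The figure matters because A.6.1 calls the trial confirmatory, A.5 intends it to substantiate a superiority claim, and A.1.1 links it to CE marking. Ethics and regulatory reviewers judge the design partly on this statement. A non-significant result would be read as coming from a trial with an 80% chance of finding a 25-point effect, when the chance was much lower.

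A smaller matter sits beside it. A relative 25% gain on 50% is 62.5%, not 75%, so A.5 and A.7 describe different effects.

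**Working it through.** **Inputs**

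- Control success p0 = 0.50; intervention success p1 = 0.75 (A.1.5, A.7)
- Allocation 1:1, total 80 enrolled (A.1.5, A.6.1)
- Dropout 20%, already inside the 80 (A.7)
- Significance level 5%, target power 80% (A.1.5, A.7)
- Sides: not stated. Two-sided is assumed, because the null is no difference and the result is reported with a 95% confidence interval. One-sided is also tried.

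**Subjects analysed:** 80 × (1 − 0.20) = 64, or 32 per arm.

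**Attempt to reproduce the 80**

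Pooled-variance formula, with mean rate (0.50 + 0.75)/2 = 0.625:

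n per arm = [1.96 × √(2 × 0.625 × 0.375) + 0.8416 × √(0.50 × 0.50 + 0.75 × 0.25)]² / 0.25²

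= [1.96 × 0.6847 + 0.8416 × 0.6614]² / 0.0625 = 57.7, so 58 per arm.

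- Total evaluable: 2 × 58 = 116
- Enrolled at 20% dropout: 116 / 0.8 = 145 (146 for equal arms)

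Unpooled variance: (1.96 + 0.8416)² × 0.4375 / 0.0625 = 54.9, so 55 per arm. That is 110 evaluable, and 110 / 0.8 = 137.5, so 138 enrolled.

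With continuity correction: 66 per arm, 132 evaluable, 165 enrolled.

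The smallest requirement under any variant tried (one-sided, unpooled, no dropout) is 88 evaluable, or 110 enrolled with 20% dropout. None gives 80.

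**Power with 32 per arm, two-sided 5%**

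Pooled: z = (0.25 × √32 − 1.96 × 0.6847) / 0.6614 = 0.109, so power = Φ(0.109) = 54.4%.

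| Method | Power |
|---|---|
| Pooled z | 54.4% |
| Arcsine | 55.3% |
| Unpooled z | 57.1% |
| Chi-square, exact enumeration | 56.3% |
| Fisher's exact | 46.0% |

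**More favourable readings** (pooled to unpooled)

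| Reading | Power |
|---|---|
| Two-sided, no dropout, 40 per arm | 64.1% to 66.7% |
| One-sided 5%, 32 per arm | 66.8% to 68.9% |
| One-sided 5%, no dropout, 40 per arm | 75.4% to 77.2% |

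**Detectable difference**

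With 32 per arm, two-sided 5% and p0 = 0.50, power reaches 80% when p1 is about 0.825 (pooled), a difference of about 33 points. The unpooled formula gives about 0.814, or 31 points.

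**The A.5 wording**

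A relative 25% gain is 0.50 × 1.25 = 0.625. Detecting 50% against 62.5% with 80% power needs 247 per arm (pooled), and 32 per arm gives about 17%. The sample size sections do not use this contrast. The figures only show that A.5 and A.7 cannot both describe the same design.

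**The case against.** The strongest defence is that the number of sides is not stated and A.5 frames a superiority hypothesis, so a one-sided test could be meant. The undirected null and the 95% interval point the other way, and one-sided power is still below 80% even with no dropout. The assumption therefore belongs in the text but does not alter the conclusion.

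Second, 80 might be a per-arm figure carried forward as a total. The continuity-corrected 66 per arm times 1.2 is 79.2, and 80 per arm would leave 64 evaluable per arm and about 84% power. This is a plausible origin but only conjecture, and the text rules it out as a reading: A.1.5 makes eighty the total, and A.6.1 treats the 80 as the whole trial. If it is how the figure arose, the slip lies in the number of subjects rather than in the power, and the sponsor is best placed to say.

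Third, A.7 speaks of at least 80, so more could be enrolled. But it also says 80 is sufficient, which is the statement in error, and A.6.1 triggers the analysis when the 80 are done.

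Finally, the relative wording in A.5 is probably loose drafting, since A.1.5 and A.7 both fix 75% against 50%. That is fair: it is a subsidiary point and adds nothing to the power shortfall.

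**Conclusion.** The power statement is wrong as written. On the protocol's own inputs, 80 enrolled with 20% dropout gives about 55% power (54% to 57% by the usual tests, 46% by Fisher's exact test) against the 80% stated. The stated target needs 116 evaluable, about 145 enrolled. The conclusion rests on a two-sided 5% test, equal arms and dropouts leaving the primary analysis; relaxing the first and assuming no dropout at all still leaves power short of 80%. The relative wording in A.5 separately contradicts the absolute 25 points in A.7.

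**What to change.** In A.1.5 and A.7, replace the power claim with what the design delivers, for example: 80 enrolled, 64 evaluable after 20% dropout, gives about 55% power for 50% versus 75% at two-sided 5%; 80% power is reached for a difference of about 33 percentage points. State next to it that 80% power for 25 points would need 116 evaluable, about 145 enrolled (146 for equal arms).

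In A.5, change the relative 25% to an absolute 25 percentage points so that the hypothesis matches A.7.

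The cost is wording in three sections and a less favourable power statement. Correcting the statement needs no extra patients. It does leave a trial labelled confirmatory at about 55% power, so the sponsor should decide openly whether to accept that, enlarge the trial, or justify a larger expected effect.
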